### III. Preliminary Studies/Progress Report: None

### IV. Research Methods

#### A. Outcome Measure(s):

Phase I Data collection. Because of the potentially sensitive nature of reproductive health behaviors, individual interviews were chosen as the first step to better elucidate and explore the issues related to pregnancy desires and contraceptive behaviors. The table below outlines the topics we will explore.

Level	Topics to Explore in Individual Qualitative Interviews
Individual	
 
➤ Pregnancy desire/motivation, perceived susceptibility/seriousness of an unintended pregnancy (impact on woman biologically, financially/economically)
 
➤ Contraceptive knowledge, perceived benefits/barriers (effectiveness, side effects) internal cues for using contraception (past counseling experience, biological issues), overall attitude toward contraception
 
➤ STI knowledge, behavior, condom use and relationship to
 

	contraceptive behaviors
Social/relationship	
 
➤ Perceived partner's knowledge and involvement in contraceptive decisions
 
➤ External cues to action - ongoing support and reinforcement for contraception
 
➤ Issues specific to different types of partners
 
➤ Familial, peer and cultural norms that influence contraception
 

Community	
 
➤ Characteristics of family planning and STI services, past experience, media messages, access and utilization of services
 

Intervention specific	
 
➤ Feedback on the core components of the intervention, specifically the role of a peer-educator and connection to services, and recommended intervention frequency/duration and suggested engagement methods
 

Information from the individual interviews will be combined with evidence from the literature to further specify the intervention. The intervention will then be operationalized by creating a manual as well as a detailed outline that will be used to solicit feedback in the focus groups. We will then conduct two focus groups with the primary aim of obtaining women's feedback on the intervention and their thoughts on the most important aspects of HBM as related to contraception decision making and behavior. Focus groups are a strong addition to our formative methods, as they provide a cost-effective method of collecting information and a social forum to further evaluate the intervention. The social forum helps to identify salient issues and weed out extreme views that may have been obtained in the individual interviews (Agar & MacDonald, 1995). It also allows participants to interact and respond to each other's ideas. This synergy will provide valuable information in further refining the intervention. After each focus group, suggestions will be reviewed and needed modifications will be made to the intervention content and structure. Additionally, during this time, processes will be explored and put in place for referral to family planning services.

**B. Phase II.** We will then recruit 160 women in OMAT to participate in this phase of the study. Quantitative study data will be collected through participant surveys at baseline, 3 months, and 6 months follow-up. We will collect baseline data on a tablet, and 3 and 6 months follow-up using RedCap. A copy of this survey is included in this application and the content is as follows:

- Demographic data: Age, religion, sexuality, living situation, partnership status, previous pregnancies length of time in treatment and number of unique episodes
- Psychosocial: Knowledge of contraceptive methods and pregnancy risk; stage of change and level of motivation to prevent unintended pregnancies, attitudes towards different contraceptive methods, self-efficacy regarding condom and birth control use, ability to engage in preventive behaviors, partner communication, pregnancy desires
- Current behavior: In last 30 days and most recent: number of partners, number of vaginal sex acts, times used contraceptives, times used condoms, partner perceptions of contraceptives and condoms, risk behaviors.

When possible, we will supplement survey data with clinical data from DH's data warehouse, including pregnancy and STI history, number of clinic visits, family planning visits, and contraceptive changes for the six month study. Additionally, we will collect biological urine and test for pregnancy at baseline. Once the biological sample is tested, all clinic guidelines related to testing and follow-up will be conducted by appropriate clinic staff.

### **Description of Population to be Enrolled:**

Study inclusion/exclusion criteria: Phase I: being female; 18-35 years of age; being in opioid medication-assisted treatment at one of our two clinic sites; not currently pregnant or trying to become pregnant; and have no known medical reason that would prevent pregnancy (e.g., hysterectomy, tubal ligation), having sex or intending to have sex with biological male (at risk of pregnancy) . Individuals who are not able to complete the interview in English, or who are intoxicated or impaired mentally to the point that they cannot voluntarily consent to participate in the project and/or respond to the interview will also be excluded.

Phase II: being female; 18-44 years of age; being in opioid medication-assisted treatment at one of our two clinic sites; not currently pregnant or trying to become pregnant; and have no known medical reason that would prevent pregnancy (e.g., hysterectomy, tubal ligation, menopause), having had sex or intending to have sex with biological male (at risk of pregnancy), and not currently using a LARC . Individuals who plan to move out of the area in the next 6 months, have a pending incarceration, and/or are not able to complete the interview in English, or who are intoxicated or impaired mentally to the point that they cannot voluntarily consent to participate in the project and/or respond to the interview will also be excluded.

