### **C. Study Design and Research Methods**

. This study will be completed in two phases The first formative phase (Aim 1) will include individual qualitative interviews with women in OMAT. These interviews will be used to elucidate and explore the barriers to effective contraceptive use and STD prevention. Findings from these interviews in conjunction with prior literature and evidence based models will be used to develop the intervention. Focus groups will then be conducted to obtain feedback on the developed intervention and a final intervention will be developed. The developed intervention will then be piloted with 10 women who are in OMAT. The second efficacy phase (Aim 2-3) will randomize subjects to the intervention or the usual care and assess outcomes 3 and 6 months post-baseline.

***Phase I qualitative and intervention development.*** Individual interviews (up to 30) and 3 focus groups (n=20) will be conducted with women in OMAT of reproductive age. Purposeful convenience sampling is considered most appropriate for formative research (Patton, 2002; Schensul, 1999). Women will be recruited from two treatment centers. *Outpatient Behavioral Health Services (OBHS)* is a stand-alone substance use treatment clinic located on the Denver Health Medical Center campus in central Denver and has dispensed methadone (ORT) and provided substance use and mental health treatment for over 30 years. *Addiction Research and Treatment Services (ARTS)* is in the Division of Substance Dependence, Department of Psychiatry, University of Colorado School of Medicine. ARTs began in 1971 as a federally funded methadone maintenance program and currently has four outpatient clinics. The Denver Clinic will serve as a treatment clinic for this study and is also located in central Denver. Clinic providers will be

asked to identify and refer eligible women to the research assistant. Participation will also be solicited from flyers hanging in the clinics. Additionally, participants may be recruited in person by the researcher. We will attempt to include representation across different ages, ethnicities, women with and without prior non-condom contraception use, and women with and without children.

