#### **D. Description, Risks and Justification of Procedures and Data Collection**

##### **Tools:**

Risks consist of potential embarrassment or discomfort in responding to sensitive questions. Participants may feel discomfort or embarrassment responding to questions about sensitive topics such as their knowledge and attitudes about reproductive health, STIs, pregnancy, and contraception. We believe this risk is low. Participants can choose not to respond to questions they are uncomfortable with. Additionally, if they are upset by the survey or have additional health related questions, we will refer them to a clinician on site (either behavioral health consultant or primary care provider/nurse). We will also provide an informational brochure at the end of the interview or focus group. The brochure will outline contraceptive methods and clinic locations.

There is a risk of loss of confidentiality but we believe this risk is low. All study data will be collected in a confidential setting and will be associated with a study ID and not with identifying information. Confidentiality cannot be assured in the focus groups participants will be informed of this risk.

As part of the study, we will collect a urine sample to test for pregnancy at baseline. If the participant received a positive pregnancy screening, they will be referred to the appropriate clinic staff, and excluded from participating in the study.

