##### **E. Potential Scientific Problems:**

In the qualitative formative work, we will use purposeful sampling, which will not be representative of all women in OMAT. However, these data will be used to inform the development of an intervention that will be tested in a second phase (to be submitted once finalized).

Participants may not represent all women in treatment in Denver. We will make every attempt to understand and correct any recruiting biases, and recruit and enroll all eligible women receiving treatment at ARTS or OBHS during the time of the study.

Retention of participants for the second session, and for the three and six month follow-up interview is the biggest potential scientific problem. We intend to ask all participants for relevant contact information so that we can find them for their follow-up session and interviews.

These data are self-reported, which comes with limitations. However, several mechanisms are being put in place to reduce this bias, including: conducting the interview in a confidential setting; ensuring data is stored in a secure location; and using software so that participants can directly enter their answers into the computer. Literacy levels may also be a concern, but we will use survey software that will allow participants to hear and see the questions simultaneously. Additionally, a researcher will be available during the interview to address any comprehension concerns.

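### Phase II eligibility does not exclude women from the Phase I focus groups, who have reviewed the intervention outline and could then be randomised, including to usual care

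*Combined protocol and SAP*

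**What the plan says.** Under Description of Population to be Enrolled, Phase I takes women "being female; 18-35 years of age; being in opioid medication-assisted treatment at one of our two clinic sites" and Phase II takes women "being female; 18-44 years of age; being in opioid medication-assisted treatment at one of our two clinic sites". Phase II also requires that a woman is "and not currently using a LARC". It adds exclusions beginning "Individuals who plan to move out of the area in the next 6 months, have a pending incarceration" and continuing with language and capacity to consent. No criterion mentions earlier participation in the study.

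Section IV.C names the same two clinics, OBHS and ARTS, for both phases. It gives the Phase I size: "Individual interviews (up to 30) and 3 focus groups (n=20) will be conducted with women in OMAT of reproductive age". Section IV.A describes the focus groups differently in number, but states their purpose: "We will then conduct two focus groups with the primary aim of obtaining women's feedback on the intervention". There the women respond to a detailed outline of the intervention. The interviews, which come earlier, cover contraceptive knowledge, benefits and barriers, and ask for views on the intervention's core components. Aim 1a in Section I adds a particular interest in LARCs.

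Section IV.D states: "We will also provide an informational brochure at the end of the interview or focus group". The brochure covers contraceptive methods and clinic locations. Section IV.E says the study will try to "recruit and enroll all eligible women receiving treatment at ARTS or OBHS during the time of the study". Under Usual Care, Section IV.C says neither clinic has standard work for assessing contraceptive use, informing women about methods or referring them.

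**The concern.** Followed as written, the plan lets a focus-group member who is not on a LARC be screened, enrolled and randomised. In usual care she does not match the comparator described, because she has already gone through an outline of what the other arm receives. Any effect of that exposure on visits or LARC uptake would raise the usual-care rate and shrink the contrast for Hypotheses 1 and 2. In the intervention arm she would contribute to the acceptability result in Aim 2 on content she helped to shape.

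In either arm, her baseline knowledge and self-efficacy scores are taken after exposure. Those scores feed the secondary statement under Hypothesis 1. If earlier participation is not recorded, none of this can be examined afterwards.

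**Working it through.** **Inputs from the documents.** Study Statistical Power (Section IV.F) gives 75 per group, 80% power, a 23-point difference and an average success rate of 50%, with non-responders counted as failures. I read this as 38.5% in usual care and 61.5% in the intervention arm. The error rate is 0.05 per comparison (Section IV.F). Sidedness is not stated, so I assume two-sided. Section IV.C gives 20 focus-group women and up to 30 interviewees.

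**The plan's own figure.** Normal approximation with pooled variance under the null:

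power = Φ{[Δ√n − 1.96√(2p̄(1−p̄))] / √[pU(1−pU) + pI(1−pI)]}

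With Δ = 0.23, n = 75, p̄ = 0.50, pU = 0.385 and pI = 0.615:

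(1.992 − 1.386) / 0.688 = 0.88, and Φ(0.88) = 81.1%. The stated 80% is reproduced.

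**Largest possible overlap.** Focus-group women: 20/150 = 13.3% (20/160 = 12.5%). Everyone in Phase I, if no woman did both activities: 50/150 = 33% (50/160 = 31%).

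**Dilution.** Let f be the share of the usual-care arm who were in a focus group, and e the share of the intervention effect that they already carry. Both are assumptions. The intervention rate is held at 61.5%, and

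pU = 0.385 + f × e × 0.23.

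With all 20 re-enrolled and split evenly, f = 10/75 = 0.133:

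| e | pU | Difference (points) | Power, 75 per group |
|---|---|---|---|
| 0 | 38.5% | 23.0 | 81% |
| 0.10 | 38.8% | 22.7 | 80% |
| 0.25 | 39.3% | 22.2 | 78% |
| 0.50 | 40.0% | 21.5 | 75% |
| 1.00 | 41.6% | 19.9 | 69% |

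A smaller overlap gives a smaller loss: f = 5% with e = 0.5 gives 22.4 points and 79%.

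**Is the gap closed elsewhere?** The nearest safeguard is in the Phase II part of Section IV.C: the first 10 recruits give feedback on the survey and intervention, and their data may be dropped. That rule is discretionary and does not cover focus-group or interview women. Assignment is pre-defined by study ID, with no stratification by earlier participation. The LARC criterion removes only those Phase I women who are using a LARC when screened for Phase II.

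**The case against.** The strongest reply is that exposure in Phase I is thin. The intervention consists of one-to-one sessions with a peer navigator, motivational interviewing, an appointment (on the same day where possible) and rescheduling after a missed visit. No Phase I activity provides navigation or an appointment, and Hypotheses 1 and 2 concern visits and LARC initiation. Women who took up and kept a LARC after Phase I are screened out. This stands. It makes the lower rows of the table less plausible, but it does not restore a naive baseline or an independent view of acceptability.

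A reader might infer that all 50 Phase I women, 31% of 160, have already received the content. The documents do not support that. The interviews precede the developed intervention and mainly elicit views, and the Phase II baseline survey asks every woman about much the same topics. The 50 also assumes that all 30 interviews took place, that no woman did both activities, and that every woman stayed eligible and willing.

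A reader might also treat the brochure as exposure peculiar to Phase I. Section IV.D does not limit it in that way, and the Phase II baseline is also called an interview, so both arms may receive it.

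Finally, the aim of enrolling all eligible women is worded as an effort. It makes re-approach of Phase I women likely, but does not guarantee it.

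**Conclusion.** The omission is real and nothing else in the document closes it. It matters mainly for the 20 focus-group women, at most about 13% of 150. Interviewees are a lesser concern. It should be corrected because the plan starts at 81% power with almost no reserve and the correction is simple.

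The size depends on two quantities that the documents do not give: how many of these women re-enrol, and how much of the effect prior exposure carries. With all 20 re-enrolled, the loss runs from about 1 point of power (e = 0.10) to about 12 (e = 1.00), the extreme case.

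A reader might infer a biased comparison between arms. Randomisation should spread former participants over both arms, so the documents support dilution and non-naive baseline scores, not systematic imbalance.

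**What to change.** 1. Add to the Phase II exclusions: took part in a Phase I focus group.
2. Record Phase I interview participation at screening, and repeat the Hypothesis 1 and 2 tests without former interviewees as a sensitivity analysis.
3. Reconcile the 10-woman pilot (Aim 1d in Section I, and the opening of Section IV.C) with the first 10 Phase II recruits. If they are the same women, exclude them from the efficacy analysis by a fixed rule instead of leaving it to discretion. For that reason, do not simply add pilot participants to the eligibility exclusions.
4. State the number of focus groups consistently (two in Aim 1c and Section IV.A, three in Section IV.C), so that the group to be excluded is well defined.

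Cost: one eligibility line, one screening question, and about 20 women removed from the recruitment pool. If other eligible women replace them, the plan keeps its 81%. If none could be replaced, (150 − 20)/2 = 65 per group would give about 75% by the same formula, so the enrolment target should be held.

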### **C. Study Design and Research Methods**

. This study will be completed in two phases The first formative phase (Aim 1) will include individual qualitative interviews with women in OMAT. These interviews will be used to elucidate and explore the barriers to effective contraceptive use and STD prevention. Findings from these interviews in conjunction with prior literature and evidence based models will be used to develop the intervention. Focus groups will then be conducted to obtain feedback on the developed intervention and a final intervention will be developed. The developed intervention will then be piloted with 10 women who are in OMAT. The second efficacy phase (Aim 2-3) will randomize subjects to the intervention or the usual care and assess outcomes 3 and 6 months post-baseline.

***Phase I qualitative and intervention development.*** Individual interviews (up to 30) and 3 focus groups (n=20) will be conducted with women in OMAT of reproductive age. Purposeful convenience sampling is considered most appropriate for formative research (Patton, 2002; Schensul, 1999). Women will be recruited from two treatment centers. *Outpatient Behavioral Health Services (OBHS)* is a stand-alone substance use treatment clinic located on the Denver Health Medical Center campus in central Denver and has dispensed methadone (ORT) and provided substance use and mental health treatment for over 30 years. *Addiction Research and Treatment Services (ARTS)* is in the Division of Substance Dependence, Department of Psychiatry, University of Colorado School of Medicine. ARTs began in 1971 as a federally funded methadone maintenance program and currently has four outpatient clinics. The Denver Clinic will serve as a treatment clinic for this study and is also located in central Denver. Clinic providers will be

asked to identify and refer eligible women to the research assistant. Participation will also be solicited from flyers hanging in the clinics. Additionally, participants may be recruited in person by the researcher. We will attempt to include representation across different ages, ethnicities, women with and without prior non-condom contraception use, and women with and without children.

The content of the individual interview has been described above and will explore salient issues related to reproductive health among women in OMAT. We will combine information from the individual interviews with evidence from the literature to develop a preliminary intervention and proposed content. We will then conduct focus groups to obtain more targeted feedback from the women on the developed intervention. The intervention will be finalized and tested in the second phase which will be submitted as an amendment.

All formative qualitative interviews will be audio-taped and transcribed into Word. The qualitative interviews will be transcribed by a consultant who is not part of the research team (used in prior studies). The digital files will be saved on ([www.box.com](http://www.box.com)) for the transcriptionist to access. This is an encrypted storage site that also provides audit logs of who accessed the files. No names will be associated with the digital recordings or transcribed files. Once the transcribed file is received, all digital recording will be removed from [www.box.com](http://www.box.com). The transcriptionists have also signed all Denver Health confidentiality paperwork. Once transcribed the word files will be transported into Atlas.ti for analysis. Once transported into Atlas the digital recording will be erased from the Denver Health server. All Atlas.ti files will contain a unique study id and no identifying information.

Focus group data will be audio-taped and the co-facilitator(s) will take extensive notes. The digital files will be reviewed and information will be added to the notes. These data will be used primarily to modify the intervention and all digital recordings will be erased after the intervention has been finalized.

***Phase II Efficacy Evaluation*** This study will be conducted at the DH Outpatient Behavioral Health Services clinic (OBHS), and at the University of Colorado's Addiction Research and Treatment Services clinic (ARTS). Potentially eligible patients will be identified by the research staff through screening the clinic schedule, and by clerical clinic staff. Patients identified as potentially eligible will be approached at the clinic during dosing hours or before/after group sessions, and asked if they would like to participate in the study. Additionally, providers will be asked to refer potentially eligible participants to the research staff. Flyers will also be hung at the clinics. All identified/referred patients will be screened for final study eligibility by a trained researcher in a confidential setting, and if eligible invited to participate in the study. If deemed eligible and interested, the participant will be consented and will complete the baseline interview electronically.

Research staff will obtain informed consent from all participants by allowing them to review the consent form, and by highlighting particularly important aspects. The baseline interview will be collected using a computerized tablet using ACASI software. ACASI is a computer/tablet-based interview and data collection instrument that automatically enters and stores the data, eliminating the data entry process. In addition, this software allows the interview to be set up so that participant simultaneously reads the questions on a tablet, and hears the questions on headphones. This method decreases problems with low literacy levels and provides increased anonymity, especially with sensitive questions. All tablets will have headphones so that each participant can hear the questions privately. A researcher will also be there to answer any questions, or help if there are any technical problems with the survey. The survey data will be associated with a study id and initially stored in an encrypted file on the tablet as the participant is completing the interview. At

the completion of the interview, the researcher will retrieve the tablet, copy the interview to a secure Denver Health network drive, and erase the file from the tablet. The researcher will then pay the participant for her time. The three and six month interview will be done online using RedCap, a secure software that is regularly used in research. A spreadsheet will be developed to manage all aspects of study data. After the baseline interview, the research assistant will assign participants into study groups based on pre-defined randomization based on study ID.

For the first 10 patients recruited, we will ask them to provide feedback on the baseline survey and intervention and this information will be used to further refine the study survey and intervention. Depending upon the changes made, data from these initial participants may be excluded from the final analyses.

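### Concealment of the ID-keyed allocation list is not described, and, separately, clinic is neither a stratum nor a pre-specified covariate

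*Combined protocol and SAP*

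**What the plan says.** All of the following is in the combined protocol and SAP.

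- **Assignment (IV.C, Phase II Efficacy Evaluation).** Once the baseline interview is done, "the research assistant will assign participants into study groups based on pre-defined randomization based on study ID".
- **Use of the ID (same section).** The ID is in use during the baseline interview: "The survey data will be associated with a study id and initially stored in an encrypted file on the tablet". The text does not say when IDs are issued or whether they run in order.
- **Recruitment (same section).** "Potentially eligible patients will be identified by the research staff through screening the clinic schedule, and by clerical clinic staff". Women are then "screened for final study eligibility by a trained researcher in a confidential setting", and research staff take consent.
- **What is not stated.** The plan does not say how the sequence is generated, whether it is blocked, who holds it, or how later assignments are hidden. It describes no stratification.
- **Pregnancy test (IV.D).** A positive baseline urine test excludes a woman. Its place relative to assignment is not given.
- **Baseline comparability (IV.F, Data Analysis Plan).** Arms are compared on baseline measures, and the regressions adjust for differences that prove statistically significant. Psychosocial variables are included; clinic is not named.
- **Clinics (IV.C).** There are two, OBHS and ARTS. OBHS stands on the Denver Health campus. The health educator who receives intervention referrals is a Denver Health employee.

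**The concern.** **Concealment.** A peer-navigator intervention cannot be masked from the women or from those who deliver it, so the protection against selection at entry is that nobody who recruits knows the next arm. If the ID determines the arm and the ID exists before assignment, assigning after the baseline interview does not by itself conceal anything. Someone holding both the ID and the key could know the arm while eligibility or consent was still open. There is room to act on such knowledge. Women are approached in person, and some entry criteria need judgement, such as intention to have sex, plans to move, and impairment. The intervention works on readiness to connect with family planning. A recruiter may sense that trait, and it bears directly on Hypothesis 1 (family planning visit) and Hypothesis 2 (starting a long-acting reversible method, LARC).

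**Clinic.** Clinic may influence how easily a woman reaches a family planning visit. An unstratified list can leave the clinics unevenly split between arms, and the analysis adjusts for that only if a baseline test happens to be significant.

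**Working it through.** **1. The plan's own figure.** IV.F gives 80% power for a 23-point difference around a 50% average with 75 per group. Two-sided 5% test, pooled variance under the null: SE0 = √(2 × 0.5 × 0.5 / 75) = 0.0816; SE1 = √(2 × 0.385 × 0.615 / 75) = 0.0795; power = Φ[(0.23 − 1.96 × 0.0816) / 0.0795] = 0.81. The figure reproduces. Neither point below depends on it, and neither fix changes the sample size.

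**2. When the arm becomes fixed.** The order in IV.C is: identify, screen, consent, baseline survey under a study ID, then assignment by a rule that depends on that ID. The arm is therefore settled once the ID is issued, at the latest during the survey. Who can read the key at that moment is not stated.

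**3. What steering could produce (all inputs assumed).** Spurious difference = (share ready, intervention − share ready, usual care) × (rate if ready − rate if not). The standard error is pooled at 75 per arm, and the last column is the chance of p < 0.05 when the intervention does nothing.

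| Outcome; rate if ready v not | Ready, intervention v usual care | Spurious difference | SE | False-positive rate |
|---|---|---|---|---|
| LARC; 30% v 5% | 30% v 20% | 0.10 × 0.25 = 2.5 points | 5.2 | about 8% |
| LARC; 30% v 5% | 35% v 15% | 0.20 × 0.25 = 5.0 points | 5.2 | about 16% |
| Visit; 60% v 20% | 30% v 20% | 0.10 × 0.40 = 4.0 points | 7.5 | about 8% |
| Visit; 60% v 20% | 35% v 15% | 0.20 × 0.40 = 8.0 points | 7.5 | about 19% |

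**4. Would the baseline check catch it?** Suppose readiness is measured perfectly as yes or no, with 75 per arm.

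- 30% v 20%: SE0 = √(2 × 0.25 × 0.75 / 75) = 0.0707; SE1 = √((0.21 + 0.16) / 75) = 0.0702; power = Φ[(0.10 − 0.1386) / 0.0702] = 0.29.
- 35% v 15%: SE0 is the same; SE1 = √((0.2275 + 0.1275) / 75) = 0.0688; power = Φ[(0.20 − 0.1386) / 0.0688] = 0.81.

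A large imbalance would usually be flagged. A moderate one would be missed about seven times in ten and so left unadjusted.

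**5. Clinic mix without strata.** Assume a 1:1 list permuted over all women. With k women from one clinic, the number X in the intervention arm is hypergeometric, and the arms differ in clinic share by (2X − k) / (N/2). The clinic split is not in the documents, so a range is shown.

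| N | Clinic split | Chance of ≥10 points | Chance of ≥15 points |
|---|---|---|---|
| 150 | 50:50 | 19% | 5% |
| 150 | 70:30 | 15% | 3% |
| 150 | 80:20 | 15% | 2% |
| 160 | 50:50 | 27% | 8% |
| 160 | 70:30 | 23% | 6% |
| 160 | 80:20 | 17% | 3% |

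Both totals are shown because the protocol gives both. The higher 10-point chances at 160 partly reflect that 10 points is then exactly 8 women. At 75 per arm a clinic difference becomes significant only at 1.96 × √(2 × 0.25 / 75) = 16 points for a 50:50 split, or 1.96 × √(2 × 0.16 / 75) = 13 points for 80:20. A 10-point imbalance would therefore not trigger adjustment. If visit rates differed by 20 points between clinics (assumed), that imbalance would move the arm comparison by 0.10 × 0.20 = 2 points.

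**The case against.** The strongest reply is that the documents do not say recruiters can see the list. A key held by someone else, or sealed envelopes numbered by study ID, would fit the same sentence. The ID is first mentioned with the survey data, after screening and consent, and assignment already follows the baseline interview. **This stands.** A reader might infer that staff can foresee the next arm, or that one small team does everything. Neither is documented: several roles are named, no team size is given for Phase II, and when IDs are issued is not stated. What remains is that no safeguard is described.

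A reader might also infer that the lack of clinic strata makes allocation predictable. It does not. Blocking within strata can raise predictability if the list is poorly concealed. Under random allocation a clinic imbalance is chance, already reflected in the standard error, so it is not confounding in the sense of bias.

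It would be too strong to say that baseline tests cannot detect selection on motivation. The baseline survey (IV, Phase II) covers stage of change and motivation, and the regressions may adjust for psychosocial differences. Step 4 shows that this helps against a large imbalance. It does little against a moderate one and nothing against readiness that a recruiter senses but the survey does not capture.

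Finally, the figures in step 3 rest wholly on assumed inputs. They show what steering could do, not that it is likely.

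**Conclusion.** Two points hold, and they should be kept apart.

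**Concealment.** The plan fixes the arm by a rule keyed to an ID that is in use before assignment, has research staff recruit and assign, and describes nothing that would hide the next arm. This is a gap in documented safeguards, not evidence of foreknowledge. If the gap were exploited to the extent assumed, the spurious effect would be about 2.5 to 5 points for LARC use and 4 to 8 points for visits, and the planned check would find the milder case about 29% of the time.

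**Clinic.** Leaving clinic out of both the allocation and the models risks a chance imbalance of 10 points or more in clinic mix with probability about 15 to 19% at 150 women (17 to 27% at 160), for assumed splits from 50:50 to 80:20. The consequence is lost precision and a covariate set that depends on baseline p-values.

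Both should be corrected. Neither invalidates the design.

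**What to change.** **Concealment.**
- Replace the ID-keyed rule with a sequence generated and held by someone not involved in recruitment, and state who that is and how it was generated.
- Use study IDs that carry no information about arm.
- Release the arm only after consent, eligibility, the baseline pregnancy test and the baseline survey are recorded.
- Use either a concealed electronic release or sequentially numbered opaque envelopes. REDCap is an option if its randomisation function is available; the documents use it only for the follow-up surveys ("We will collect baseline data on a tablet, and 3 and 6 months follow-up using RedCap"), so a link to completion of the tablet baseline would have to be set up.

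**Clinic.**
- Stratify allocation by clinic (OBHS, ARTS) with randomly varying block sizes. Keep the block sizes from recruiting staff, so that stratifying does not weaken concealment.
- Pre-specify clinic as a factor in the Hypothesis 1 and Hypothesis 2 models, whatever the baseline tests show.

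**Cost.** A small amount of set-up, a short protocol change and one extra model term. The sample size does not change.
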